The gold standard for improving the appearance of photoaging and hyperpigmentation (specifically solar lentigines) has been a hydroquinone-containing product. Makino et al compared Lytera 2.0 (a Correcting Serum) to Hydroquinone 4% in a randomized, split-face double blind study in subjects with moderate to severe skin tone. Lytera 2.0 showed statistically significant results at 2 weeks and Hydroquinone 4% showed statistically significant results at 4 weeks. Lytera 2.0 is a cosmetic product that is for brightening the appearance of skin does not contain any hydroquinone or other ingredient classified as a drug. (Please see the Lytera 2.0 patient brochure in the attached documents).The 1927 nm fractional non-ablative

laser has also been found to be effective in treating the pigment in photo-damaged skin.

In our study, only patients with Fitzpatrick skin types I through IV will be recruited as those with a higher level than skin type IV can be prone to overproduction of melanin following certain laser types. Fitzpatrick skin type I is highly sensitive, always burns, and never tans. Type II is very sun sensitive, burns easily, and hardly tans. Type III is sensitive, sometimes burns, and tans to light brown. Type IV is minimally sun sensitive, burns minimally, and tans to moderate brown. Type V is insensitive skin, rarely burns, and tans well. Type VI is insensitive, never burns, and is deeply pigmented.

Although laser treatment and lightening skin care products have been shown to improve skin tone and photo aging, currently, there is no clinical data to support the efficacy and longevity of combination laser treatment + brightening skin care products for photoaging and skin tone. Our study will attempt to observe if combination non-ablative laser (1927 nm also known as Clear and Brilliant) and Lytera 2.0 Correcting Serum will improve the appearance of skin tone and photoaging when compared to laser alone.

4) Inclusion and Exclusion Criteria*

Inclusion criteria:

- Healthy adult male and female patients 18 years and older
- Fitzpatrick skin types I-IV
- Has at least mild mottled skin tone of the face (score of 2 or more on a 5 point skin tone scale)
- Has at least 2 areas of the face with significant roughness, dyspigmentation, or fine lines or has all these characteristics in 1 or more areas

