	Screening/Baseline Visit 1	Washout period	Visit 2 First Laser treatment (4 weeks +/- 5 days after baseline visit)	Visit 3 Second Laser Treatment (3 weeks +/- 5 days after first laser treatment)	Visit 4 Last day of topical treatment (4 weeks +/- 5 days after second laser treatment)
Procedures					
Informed Consent	X				
Inclusion/Exclusion criteria	X				
Demographic History Questionnaire	X				
Medical History Review	X				
Skincare History Review	X				
Evaluate Fitzpatrick skin type	X				
Evaluate baseline hyperpigmentation	X				
Urine dipstick test	X		X	X	X
Self assessment questionnaire	X				X
Standardized Digital photography	X		X	X	X
Adverse effects review	X		X	X	X
MoPASI evaluation	X		X	X	X
GAIS evaluation	X		X	X	X
Anesthetizing topical application			X	X	X
Protective goggles placed			X	X	
Laser treatment performed			X	X	
Exit Questionnaire					X

Potential participants will receive a thorough history and dermatologic physical exam to determine if patients meet the inclusion/exclusion criteria for being in the study. Urine dipstick tests will be performed on female

patients to confirm they are not pregnant. Consent will be obtained from eligible participants and will be enrolled in the study.

The study will be conducted over a 12 week period. There will be a 4 week washout period prior to laser treatments when the subjects will begin two skin care regimens, which are described below. Then there will be 2 laser treatments separated by 3 weeks. The subjects will continue the topical treatment 1 month after the 2nd laser treatment.

There will be 4 study visits: Baseline Visit 1, First laser treatment Visit 2 (4 weeks +/- 5 days after baseline visit), Second laser treatment Visit 3 (3 weeks +/- 5 days after first laser treatment), and Last day of topical treatment Visit 4 (4 weeks +/- 5 days after second laser treatment). During these visits, photographs of the participants' faces will be taken. Patient questionnaires will be given at baseline and at the end of the study.

Investigators will complete the study 4 months after subjects have completed their participation in the study.

8) Study Endpoints*

The study will reach endpoint for each patient either 1) once they have completed their exit survey after the 2 laser treatments and the topical treatments or 2) if they experience any adverse reactions from treatment and must be pulled from the study.

9) Procedures Involved*

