One month prior to laser treatments (washout period), 14 male and female subjects with moderate hyper pigmentation and photo damage of the face will be randomized to 2 skincare regimens.

The regimens are:

- "Placebo arm" – Basic skin care regimen* (Facial Cleanser, TNS ceramide Treatment Cream (standard post-procedure moisturizer), and Essential Defense Mineral Shield Broad Spectrum SPF35 (all-physical sunscreen))
- "Lytera arm" – Basic skin care regimen + **Lytera 2.0**, which will be added between the Facial Cleanser and TNS Ceramide Treatment Cream

*The basic skin care regimen is a standard regimen used in several skincare product experiments

After cleansing the face, the patients in the Lytera arm will apply one pump of the pigment-correcting serum in a circular motion to the entire face

including the forehead, cheeks, chin, nose, and neck with care to avoid the eyes. The Lytera 2.0 is applied prior to applying moisturizer and sunscreen.

On laser treatment days, patients will come into the office without having applied any topical cream that day. Lidocaine topical may or may not be applied over the face avoiding the eyes (lidocaine use will be at discretion of Principal Investigator), and patients will be given protective goggles to shield the eyes during laser treatment. Next, the laser wand is pressed to the face and passed over the skin in various horizontal and vertical directions. Treatment takes 20 to 30 minutes.

Standardized digital photographs will be taken at baseline and at each subsequent visit using the Canfield VISIA Complexion Analysis (VISIA-CA) camera system at the highest resolution in a consistent position. Pictures will be taken before laser treatments on Visit 2 and Visit 3.

The subjects will complete an exit questionnaire after completion of the study at their last study visit (Visit 4). Through the questionnaire, we will obtain information on subject satisfaction with the study as well as their opinion of how their skin has changed. We hope to use the responses to assess efficacy of our skincare regimen and to improve future related research protocols.

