Phenylethyl Resorcinol

Niacinamide and Tetrapeptide 30

Marinen Extract blend

Phytic Acid

Other ingredients: Vitis Vinifera SCE, Plankton Extracts, Hydroxyacetophenone, Artemisia Capillaris, Marine Exopolysaccharides

Data that will be collected about subjects (see attached data collection form):

Age

Gender

Race

Past medical history including current and past illnesses, current medications, allergies, past surgeries, any past adverse effects to facial cosmetics, family history, social history including alcohol, tobacco, or illicit drug use.

Past skin care history including any surgical cosmetic procedures, fillers, injectables, lasers, or topical treatments.

Fitzpatrick skin type (I-IV)

Evaluation of baseline skin tone

Adverse effects experienced throughout the study

MoPASI scores

GAIS scores

Representative photographs of subjects at baseline and at subsequent visits

10) **Data and Specimen Banking***

Data will be stored on Box, a secure file sharing, storage, and collaboration system using a password-protected, encrypted laptop. Data will be stored for 1 year after the completion of the study. Only [name], principal investigator and [name] and [name], co-investigators and study coordinator will have access to the data. Data will only be released by Drs. [name] or [name] for publication of study results.

Stored data will include:

Age

Gender

Race

Past medical history including current and past illnesses, current medications, allergies, past surgeries, any past adverse effects to facial cosmetics, family history, social history including alcohol, tobacco, or illicit drug use.

Past skin care history including any surgical cosmetic procedures, fillers, injectables, lasers, or topical treatments.

Fitzpatrick skin type (I-IV)

Evaluation of baseline skin tone

Adverse effects experienced throughout the study

MoPASI scores

GAIS scores

Representative photographs of subjects at baseline and at subsequent visits

11) **Data Management***

Statistical analysis will be conducted to determine the effect size necessary to power a study. All statistical tests will be two-sided and interpreted at a 5% significance level. The primary analyses will be based on the MoPASI and GAIS scores. Scores after each laser treatment will be compared to baseline scores using the appropriate statistical test.

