Data will be secured and stored on Box, a secure file sharing, storage, and collaboration system using a password-protected, encrypted laptop.

Information that will be included in data include demographic information, skin type, baseline hyper pigmentation, adverse effects, validated scale scores, photographs, past medical and skin care history as listed above.

Data will be stored in Excel sheet on the encrypted system, Box, which will

give us access to the data via an encrypted stream of traffic. No actual copy of the data will be stored on a machine. Data will be stored for a short-term retention period of 5 years or less at the location [name]. The principal and co investigators will have access to the data. Drs. [name] and [name] will be responsible for transmission of data. Data will be transported via laptop. Aforementioned laptop will be completely shut down after all browser data has been cleared before being transported or left unattended. In addition to the data encryption, a passcode into the device will be required.

12) Provisions to Monitor the Data to Ensure the Safety of Subjects*

The physician investigators and the subjects themselves will monitor the type, severity, duration, and frequency of adverse effects during treatment. Adverse effects will be evaluated by investigator at each visit. Subjects will fill out diary while at home to record any adverse effects. Investigator will be accessible to subjects via email and phone to answer questions about any adverse effects. Safety data and efficacy data (based off of validated scale scores) will be reviewed after each visit. Safety information will be collected at study visits and by email communication with participants. Safety data collection will begin on day 1 of the washout period when subjects begin the skin care regimen. The investigators will review the data at each visit and as needed. Safety information that will be collected includes pain, visual disturbance, rash, fever, infection, photosensitivity, scarring, and changes in skin color.

If a patient becomes pregnant, develops severe post-inflammatory skin tone, or experiences an anaphylactic or other severe allergic reaction, they will be pulled from the study. If they exhibit any of the "exclusion criteria" after initial evaluation of eligibility for participation in study, they will also be removed from the study.

13) Withdrawal of Subjects*

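### Change from Visit 1 to the post-laser visits includes four weeks of topical treatment before any laser, and the pre-laser Visit 2 scores have no named analysis

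*Combined protocol and SAP*

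**What the plan says.** Section 11 bases the primary analyses on MoPASI and GAIS and gives one comparison: "Scores after each laser treatment will be compared to baseline scores using the appropriate statistical test". It names no contrast between arms and no test.

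The timing comes from other sections:

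- **Start of the regimens.** Section 7 (Study Timelines): "There will be a 4 week washout period prior to laser treatments when the subjects will begin two skin care regimens". Section 12 agrees: "Safety data collection will begin on day 1 of the washout period when subjects begin the skin care regimen". Section 9 also places randomisation one month before the laser treatments.
- **What is randomised.** The arms differ only in the serum, "which will be added between the Facial Cleanser and TNS Ceramide Treatment Cream" (Section 9). Laser is common to both arms.
- **Visits.** Visit 1 is the screening and baseline visit. Next come "First laser treatment Visit 2 (4 weeks +/- 5 days after baseline visit") and "Second laser treatment Visit 3 (3 weeks +/- 5 days after first laser treatment"). Visit 4 follows the second laser by 4 weeks, again with a 5-day window.
- **Photographs and scores.** Section 9: "Pictures will be taken before laser treatments on Visit 2 and Visit 3". The Section 7 table schedules MoPASI and GAIS at all four visits, and Section 9 has the photographs graded at baseline and weeks 5, 8 and 12.

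The hypothesis in Section 2 is between arms: laser with the brightening product against laser without it.

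**The concern.** A score described as coming after laser, set against baseline, invites the reader to credit the change to laser or to the laser period. Here the baseline precedes more than laser. Between Visit 1 and the first laser, participants give up other facial products (Section 4) and use their assigned regimen for about four weeks. Any change in that time is carried into every later comparison with Visit 1.

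The protocol gives a reason to expect such change. Section 3 reports of an earlier study that "Lytera 2.0 showed statistically significant results at 2 weeks", which is shorter than the lead-in.

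Two things are at stake. First, a pre-post change cannot show how much of the improvement was already present before any laser, although the Visit 2 photographs would show it. Second, Section 11 says the analysis is to determine the effect size needed to power a study. An effect size taken from pre-post change does not address the between-arm hypothesis and cannot be divided into pre-laser and laser-period parts.

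**Working it through.** The plan gives no figure to reproduce on this point, so the check is one of visit timing.

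**Inputs (Section 7).** Visit 1 to Visit 2: 28 days (23 to 33). Visit 2 to Visit 3: 21 days (16 to 26). Visit 3 to Visit 4: 28 days (23 to 33).

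**Nominal calendar.** The visits fall at days 0, 28, 28 + 21 = 49 and 49 + 28 = 77, that is weeks 0, 4, 7 and 11. Counting baseline as week 1 gives weeks 5, 8 and 12, which matches the grading schedule. Week 5 is therefore Visit 2, before the first laser.

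**Which scores come after laser.** Photographs precede treatment at Visits 2 and 3. Visit 3 thus follows one laser session and Visit 4 follows two. Visit 2 follows none, so the sentence in Section 11 does not cover it.

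**Share of the interval before any laser** = (days from Visit 1 to Visit 2) / (days from Visit 1 to the visit in question).

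- Visit 3: 28/49 = 57%. Across the windows: 23/(23 + 26) = 47% to 33/(33 + 16) = 67%.
- Visit 4: 28/77 = 36%. Across the windows: 23/(23 + 26 + 33) = 28% to 33/(33 + 16 + 23) = 46%.
- Measured from Visit 2, the share is 0% at both visits.

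**Illustration of a pre-post test.** The documents give no MoPASI or GAIS variability, so the effect sizes here are assumptions. Suppose laser does nothing, the lead-in produces a mean change of d standard deviations of the paired differences, and that change persists. A two-sided 5% paired t test within one arm (n = 7, 6 degrees of freedom) has noncentrality d × √7:

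- d = 0.5: noncentrality 1.32, probability of significance 0.20
- d = 0.75: noncentrality 1.98, probability 0.39
- d = 1.0: noncentrality 2.65, probability 0.60

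Measured from Visit 2, with no further change, the probability is the nominal 0.05. A significant result against Visit 1 therefore need not involve laser.

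**Precision of the between-arm contrast.** At 7 per arm, two-sided 5% and 80% power, the detectable standardised difference is (1.96 + 0.84) × √(2/7) = 1.50, or 1.63 using the t distribution, before any gain from baseline adjustment.

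**The case against.** The strongest reply is that serum is the only randomised difference, and Section 2 asks what adding it does when both arms receive laser. Serum benefit gained in the lead-in belongs to the strategy being tested, so a difference already present at Visit 2 still answers the question. Stopping earlier products happens in both arms and, in expectation, does not bias the randomised comparison. All of this stands. Visit 1 is the right baseline for the between-arm effect, and Visit 2, which follows randomisation, should not replace it.

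The reply also disposes of several stronger readings that a reader might infer:

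- **That 36% to 57% of the between-arm difference pre-dates laser.** This would need benefit to accrue evenly over time, and the documents give no time course against the basic regimen.
- **That the trial will report a laser effect.** No section states that as an objective. The risk lies in how a pre-post result would be read.
- **That the cited study establishes a serum effect over the basic regimen by week 2.** Section 3 describes a split-face comparison with hydroquinone and does not say what the 2-week result was measured against. It makes early change plausible and no more.
- **That the Visit 2 scores will be discarded.** The plan simply names no analysis of them. Section 12 mentions reviewing scale scores after each visit, but as monitoring.
- **That Sections 7 and 9 contradict each other.** They agree on when the regimens start; washout is an incomplete label.

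Two limits on the remedy also stand. After Visit 2 the Lytera arm continues the serum, so its change from Visit 2 is not a pure laser effect. GAIS grades change, so a new reference point would mean grading the photographs again. Neither limit rescues the comparison in Section 11, which contains no between-arm contrast.

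**Conclusion.** The point holds as one of attribution and of a missing contrast. The stated comparison cannot be read as a laser-period effect and does not by itself test the trial's hypothesis. The calendar shares are exact at nominal timing (57% to Visit 3, 36% to Visit 4) but measure time, not effect or bias. The test probabilities of 0.20 to 0.60 rest on assumed lead-in changes and on zero laser effect; they show direction only.

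The documents do not support a claim that the randomised comparison from Visit 1 is biased. Nor could Visit 2 establish that serum and laser act together, since neither arm goes without laser. What Visit 2 can show is whether the arms already differed before any laser, and the plan does not currently provide for that. With 7 per arm, the estimates will be imprecise.

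**What to change.** Amend Section 11 as follows.

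1. Estimate the between-arm MoPASI difference at Visits 2, 3 and 4, each adjusted for the Visit 1 score and reported with a confidence interval.
2. Name Visit 4 as the main time point. This is my choice, made to limit multiplicity; the plan does not name one. Treat Visit 2 as a descriptive pre-laser contrast.
3. Do not adjust the arm comparison for Visit 2, because it follows randomisation.
4. Reference any MoPASI statement about change after laser to Visit 2, and state that in the Lytera arm this change still includes continued serum.
5. Leave the GAIS reference as it is unless the photographs are to be graded again.
6. In Sections 7, 9 and 12, describe the four weeks before laser as a topical lead-in, and not only as a washout.

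The cost is wording. The Visit 2 photographs and MoPASI scores are already scheduled, and neither the sample size nor the visit schedule changes. Only optional re-grading of GAIS would add work.

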- Willing to refrain from using any other topical products on the face, systemic retinoids, or steroids, facial peels or other facial laser procedures throughout the duration of the study
- Willing to refrain from any cosmetic procedure including but not limited to facial surgery, dermal fillers, and neuromodulators for the duration of the study
- Willing to use only the facial skin care product regimen provided for the study
- Willing to avoid extended periods of sun exposure and the use of tanning beds during the study
- Willing to have photographs taken of the face to be used de-identified in evaluations, publications, and presentations
- For females: proof that they are not pregnant (urine pregnancy test)
- English-speaker

Exclusion criteria:

- Has any uncontrolled systemic disease (such as autoimmune disorders and

connective tissue disorders such as lupus erythematosus or Sjogren's syndrome
Has any active infection in face
Has history of any skin conditions that could interfere with treatment
Has used self-tanner recently
Is currently participating in another drug research study
Is NOT willing to refrain from using any other topical products such as skin lightening, retinoids, alpha/beta-hydroxyl acids, salicylic acid, vitamins C or D, steroids, or antibiotics on the face or systemic retinoids, steroids, facial peels, neuromodulators, dermal fillers, facial surgery, or other facial laser procedures throughout the duration of the study
For females: is pregnant
Non English-speaker

Individuals will be screened for eligibility via questionnaires that address each of the inclusion and exclusion criteria. Our final study sample will include the subjects who met the inclusion/exclusion criteria and did not voluntarily drop out of the study or develop adverse effects that prohibited them from safely completing the study. We will exclude adults unable to consent, patients under the age of 18, pregnant women, and prisoners.

5) Number of Subjects*

After recruiting our subjects, 14 patients will be randomized into either arm of the study (7 in each arm).

6) Study-Wide Recruitment Methods*

This is a single center study. We will recruit subjects from a clinical database of the practice of [name]. We will use several recruitment methods including invitation via a scripted email providing information describing the study protocol and end-points, scripted invitation telephone calls, and flyers.

7) **Study Timelines***

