If a patient becomes pregnant, develops severe post-inflammatory skin tone, excessive scarring, burning, or experiences an anaphylactic or other

severe allergic reaction or infection requiring antibiotic treatment, they will be pulled from the study.

If they exhibit any of the “exclusion criteria” after initial evaluation of eligibility for participation in study, they will also be removed from the study.

Exclusion criteria:

Has any uncontrolled systemic disease (such as autoimmune disorders and connective tissue disorders such as lupus erythematosus or Sjogren's syndrome

Has any active infection in face

Has history of any skin conditions that could interfere with treatment

Has used self-tanner recently

Is currently participating in another drug research study

For females: is pregnant

Non English-speaker

Participants that develop criteria for withdrawal from the study or any potential side effect will be examined in the office. Participants that meet criteria for withdrawal from treatment will be informed during office visit. Safety information will still be collected until week 12 of the study.

14) Risks to Subjects*

Side effects of Lytera topical include stinging or tingling on application, redness, and general irritation in those with sensitive skin.

There are some expected side effects of the Clear and Brilliant facial laser procedure. These may include discomfort, redness, swelling, heat sensation, dark spots, flaking, itching, acne formation, herpes simplex reactivation, blistering, and dryness. Patients can expect facial redness immediately after treatment that commonly resolves within a few hours but may last until the next day in some patients. Possible risks or complications associated with this facial laser procedure include bleeding or crusting, burns, scarring, pigment changes, infection, and eye injury. It has been shown that adverse effects typically resolve without discontinuation of the products. There may be psychological risks associated with treatments as patients may feel self-conscious about erythematous face for a couple days

after the laser treatments. If subjects experience any of the aforementioned side effects, this may also be distressing.

Potential risks of combination Clear and Brilliant laser and Lytera treatment include all of the side effects listed above.

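### Removing randomised subjects for exclusion criteria that are not toxicity loses their efficacy outcomes and can bias the comparison of arms in an unknown direction

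*Combined protocol and SAP*

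**What the plan says.** Sections 12 and 13 each contain two removal rules. The first covers pregnancy and named harms. The second is the same in both sections: "If they exhibit any of the 'exclusion criteria' after initial evaluation of eligibility for participation in study, they will also be removed from the study". Section 12 does not list the criteria. Section 13 restates them directly below the rule, including "Has used self-tanner recently" and "Is currently participating in another drug research study".

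Section 4 has one more exclusion item, beginning "Is NOT willing to refrain from using any other topical products such as skin lightening, retinoids" and going on to peels, fillers, neuromodulators and other procedures. The Section 13 list omits it.

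On follow-up after withdrawal, Section 13 says "Safety information will still be collected until week 12 of the study"; it does not mention photographs or MoPASI and GAIS scores. Section 4 defines the sample: "Our final study sample will include the subjects who met the inclusion/exclusion criteria and did not voluntarily drop out of the study", with a further condition that no adverse effect prevented safe completion. The protocol gives no intention-to-treat set, missing-data method or dropout allowance.

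Randomisation takes place about one month before the first laser treatment (Section 9), with 14 subjects, 7 per arm (Section 5). Section 8 recognises only two ways for a subject to reach the end of the study: completion, or an adverse reaction that forces removal. Removal for a non-toxicity criterion is neither.

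**The concern.** Most exclusion criteria are conditions of entry. Used as grounds for removal after randomisation, they end outcome assessment for events that need not be harms. Whether a subject uses self-tanner or joins another drug study may depend on how the skin is responding, and possibly on the assigned arm. The subjects who remain are then no longer the groups that were randomised.

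The self-tanner trigger also calls for judgement, because the protocol does not define how recent the use must be. Section 12 has the investigators reviewing efficacy as well as safety data after each visit, so the judgement may be made with knowledge of the scores.

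The hypothesis in Section 2 is a contrast between arms, and Section 11 says the analysis is meant to inform the effect size for powering a study. Selective loss in this pilot would carry over into that later design.

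**Working it through.** The plan gives no SD, effect size, power or dropout rate, so it has no figure of its own to reproduce beyond 7 + 7 = 14. Everything below is in SD units of an improvement score (higher is better). The number removed, k, the difference delta and the removal risks are assumptions.

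**Weight of one subject.** 1/7 = 14% of an arm.

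**Shift in the contrast.** Let R be the mean of the retained subjects in an arm, X the mean of those removed, and delta = R - X. The full-arm mean is [(7 - k)R + kX]/7, so removal moves the arm mean by R minus that quantity, which is (k/7) × delta. If all removals are in one arm, the contrast moves by the same amount:

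- k = 1: 0.14 × delta
- k = 2: 0.29 × delta, or -0.29 to +0.29 SD for delta from -1 to +1 SD
- k = 3: 0.43 × delta
- 2 removed from control and 1 from the serum arm, same delta: (2/7 - 1/7) × delta = 0.14 × delta
- equal numbers with the same delta in each arm, or delta = 0: no shift

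**Worst case.** If exactly the lowest 1 or 2 of 7 normally distributed responses leave, simulation with 400,000 draws gives a rise in that arm's mean of 0.226 or 0.422 SD with no true effect. For two removals this corresponds to delta = 0.422 × 7/2 = 1.48 SD, which is outside the ±1 range above.

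**Precision.** The 95% half-width for the arm difference is t(0.975, 7 + n - 2) × √(1/7 + 1/n):

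- n = 7: 2.179 × 0.5345 = 1.16 SD
- n = 6: 2.201 × 0.5563 = 1.22 SD
- n = 5: 2.228 × 0.5855 = 1.30 SD

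The effect detectable with 80% power (two-sample t-test, two-sided 5%) goes from 1.63 SD (7 v 7) to 1.71 (7 v 6) and 1.82 (7 v 5).

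**Chance that the rule is used at all.** With an assumed removal risk per subject of 5%, 10% or 20%, equal in both arms, the chance of at least one removal is 1 - 0.95^14 = 51%, 1 - 0.90^14 = 77% or 1 - 0.80^14 = 96%. The chance that the two arms lose different numbers is 44%, 62% or 73%.

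**The case against.** Four points can be made for the plan.

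*Removal protects the measurement.* Self-tanner alters the colour in the photographs from which pigment darkness is scored, and another lightener could mimic the serum. This stands: keeping such subjects has a price. If a retained control gained the full benefit of the serum, the contrast would shrink by 1/7 per subject. For a true effect of 1.63 SD that is 1.63/7 = 0.23 SD for one subject and 0.47 SD for two, comparable to the worst-case selection bias. The answer is to keep the scores and examine the influence of the affected ones; removal leaves nothing to examine.

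*Data may not be lost.* Nothing says that photographs already taken are discarded, and a subject removed by the investigator did not drop out voluntarily. That is a fair reading of part of the Section 4 sentence. But the same sentence requires that the criteria were met, and no efficacy assessment is promised after removal, so the later scores are missing either way.

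*The direction is not known.* A reader might infer that controls, who are given no listed vehicle serum, are likelier to seek other products and be removed. That is plausible, but the documents give no rates by arm, call this arm a placebo arm, and list serum irritation, which could cause losses in the other arm. Nor is the sign fixed within an arm: losing poor responders among controls would flatter control, while losing controls helped by another brightener would do the reverse.

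*The broadest trigger is uncertain.* A reader might take the rule to remove anyone no longer willing to avoid other facial products. That item is absent from the Section 13 list and concerns willingness, not use, so the documents do not settle the matter. The point rests on the two triggers listed in Section 13, one of which is limited to drug research studies.

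**Conclusion.** The point holds in this form: as written, the plan requires removal after randomisation for events that are not toxicity, does not provide for their later efficacy outcomes, and restricts the sample accordingly. The contrast between arms can then be biased by an amount and in a direction that the documents do not fix.

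Under the assumptions above, two removals from one arm shift it by -0.29 to +0.29 SD, or by about 0.42 SD in the extreme case. Against a half-width of 1.16 SD, a shift of 0.29 SD is 0.29/1.16 = 25%. Sampling error therefore remains the larger uncertainty in this pilot, but the shift would pass unmarked into the effect size carried forward.

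Two stronger readings are not supported. The documents do not show that removals would be concentrated in the control arm, so the 0.42 SD is a bound for one pattern, not an expected bias. Nor do they show that mixing kinds of removal spoils the tolerability result: Sections 9 and 12 assess tolerability and adverse effects separately at each visit and by diary. The point merits a change before recruitment but does not invalidate the design.

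**What to change.** 1. Reconcile the exclusion criteria in Sections 4, 12 and 13, stating whether unwillingness to avoid other products is a ground for removal, and bring Section 8 into line.
2. In Sections 12 and 13, separate stopping a regimen from ending outcome assessment. Which events end laser or topical treatment, and which criteria bear on safety, stays with the investigators.
3. For subjects who meet an exclusion criterion after randomisation and still consent, keep the scheduled photographs and MoPASI and GAIS scoring to week 12, and record the deviation.
4. Amend the final-sample sentence in Section 4 so that the main between-arm analysis includes all randomised subjects in their assigned arms. Section 11 names only comparisons with baseline, so the between-arm analysis must be stated there too. Changing Sections 12 and 13 alone would leave Section 4 in conflict.
5. Report removals and deviations by arm, with reasons.
6. Add a sensitivity analysis that excludes scores affected by self-tanner or other product use.

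The cost is an amendment to these sections. Visits and photographs are already scheduled, and scoring is done retrospectively from the photographs, so no new visits are needed. The downside is the possible dilution and photographic contamination described above, which item 6 is meant to expose. With 7 per arm, that analysis will be imprecise.
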